2.3.2 Known Potential Benefits

The benefits of the study lie primarily in the opportunities to science and humanity. No direct personal benefit from participation in the study can be guaranteed, as the vaccine may or may not confer protection in humans.

3 OBJECTIVES AND OUTCOME MEASURES

3.1 Study Objectives

Primary:

1. To assess the safety and tolerability of a single intranasal dose of either 10^7 or 10^9 colony forming units (CFU) of lyophilized BPZE1 vaccine.

Secondary:

1. To assess the humoral immunogenicity of lyophilized BPZE1 vaccine at Day 15, Day 29 and Day 181 following receipt of one intranasal dose of 10^7 or 10^9 CFU of BPZE1.
2. To assess mucosal immunogenicity of lyophilized BPZE1 vaccine at Day 29 and Day 181 following receipt of one intranasal dose of 10^7 or 10^9 CFU of BPZE1.
3. To evaluate nasal clearance of BPZE1 by culture at Day 29 (and if still positive, at Day 46) following receipt of one intranasal dose of lyophilized BPZE1 vaccine of 10^7 or 10^9 CFU of BPZE1.

3.2 Study Outcome Measures

3.2.1 Primary Outcome Measures

1. Occurrence of solicited local and systemic reactogenicity from the time of the study vaccination through 14 days post-vaccination
2. Occurrence of unsolicited non-serious adverse events from the time of the study vaccination through 28 days post-vaccination
3. Occurrence of serious adverse events (SAEs) and new onset chronic medical conditions (NOCMCs) from the time of the study vaccination through approximately Day 181 post vaccination
4. Occurrence of adverse events of special interest through approximately Day 29 post vaccination

3.2.2 Secondary Outcome Measures

1. Humoral Immune Response
 - Geometric mean titers (GMTs) by serum IgG and IgA ELISA to PT, FHA, PRN, FIM 2/3 on Days 1, 15, 29, and 181

-
- Geometric mean fold rise (GMFR) by serum IgG and IgA ELISA to PT, FHA, PRN, FIM 2/3 on Days 15, 29 and 181 relative to baseline (Day 1)
 - The proportion of subjects that achieve seroconversion (defined as ≥ 2 -fold rise from baseline) to individual pertussis antigens (PT, FHA, PRN, and FIM 2/3) by serum IgG or IgA ELISA at Days 15, 29, 181 or any time point relative to baseline (Day 1)
 - Proportion of subjects achieving seroconversion (serum IgG or IgA ELISA) to one or more pertussis antigens at Days 15, 29, 181 or any time point, relative to baseline (Day 1)
 - Proportion of subjects achieving seroconversion (serum IgG/IgA ELISA) to two or more pertussis antigens at Days 15, 29, 181 or any time point, relative to baseline (Day 1)
2. Mucosal Immune Response
- Geometric mean titer ratios (GMTRs) and ratio of antigen-specific IgA ELISA (PT-IgA, FHA-IgA, PRN-IgA, FIM-IgA) to total IgA by nasal aspirate at screening, and Days 29 and 181.
 - Fold rise of the ratio of antigen-specific IgA (PT-IgA, FHA-IgA, PRN-IgA, FIM-IgA) to total IgA by nasal aspirate from the screening visit to Days 29 and 181
 - The proportion of subjects that achieve seroconversion (defined as ≥ 2 -fold rise of the ratio from baseline) to individual pertussis antigens (PT, FHA, PRN, and FIM 2/3) by nasal aspirate IgA ELISA at Days 29 and 181 or any time point relative to baseline (screening)
 - Proportion of subjects that achieve seroconversion (≥ 2 -fold rise of the ratio from baseline) to at least 1 antigen (PT, FHA, PRN, or FIM 2/3) by nasal aspirate IgA ELISA from the screening visit to Days 29 and/or 181.
3. Proportion of subjects with detectable *B. pertussis* from nasopharyngeal cultures at Day 29.
- For those who remain positive at Day 29, the subjects with detectable *B. pertussis* at Day 46 will also be evaluated and reported. Detection of *B. pertussis* in culture will be assumed to be due to study-product administration.

4 STUDY DESIGN

This is a phase 2a, single center, randomized, partially blind, placebo controlled, clinical trial evaluating a single intranasal dose of either 10^7 CFU or 10^9 CFU of BPZE1 in healthy adults (18-49 years of age, inclusive). The study will evaluate a lyophilized formulation of the product, with the goal of testing for the optimal dose for subsequent clinical trials. Since it is anticipated that the VaxINator device will be the primary mechanism of delivery in subsequent clinical trials, the majority of volunteers will receive vaccine or placebo via VaxINator device. Five individuals will receive 10^9 CFU of BPZE1 by needleless tuberculin syringe in order to compare immunogenicity to previous Phase 1 clinical trials of BPZE1.

We anticipate that enrollment will require approximately 12 months, with each subject participating for 6 months. Fifty healthy adults, 18-49 years of age will be randomized to one of four treatment groups in a 3:3:3:1 ratio, as described in the table below. Safety will be assessed through an Independent Safety Monitor (ISM) and a Safety Monitoring Committee (SMC) described in [Section 9.6](#).

Table 2: Treatment Groups and Intranasal Vaccine to be Administered

| Group | N | Intranasal Vaccination | Device Used for Administration |
|-------|----|------------------------|--------------------------------|
| 1 | 15 | BPZE1 10^7 CFU | VaxINator |
| 2 | 15 | BPZE1 10^9 CFU | VaxINator |
| 3 | 15 | Placebo | VaxINator |
| 4 | 5 | BPZE1 10^9 CFU | Needleless Tuberculin Syringe |

5 STUDY ENROLLMENT AND WITHDRAWAL

Approximately 50 healthy male and non-pregnant female subjects 18-49 years of age, inclusive, who meet all eligibility criteria will be enrolled in this study from one VTEU site. Enrollment will occur over an approximately 6-month period, and the target population will be the general Nashville community. Information regarding this study may be mailed or emailed to subjects who have previously participated in vaccine trials conducted at the VTEU site; other forms and/or mechanisms of recruitment may also be used. The local IRB will approve all materials prior to use.

Subject eligibility criteria must be assessed by a study clinician licensed to make medical diagnoses and listed on the Form FDA 1572 as the site PI or sub-investigator.

No exemptions are granted on Subject Inclusion or Exclusion Criteria in DMID-sponsored studies. Questions about eligibility should be directed toward the DMID Medical Officer. Subjects otherwise eligible with grade 1 abnormalities in hematology or chemistry values may be considered for enrollment if, in the opinion of the investigator (or clinician on the 1572), the abnormalities are not clinically significant and do not pose additional risk to the study or the volunteer.

5.1 Subject Inclusion Criteria

Subjects eligible to participate in this study must meet all inclusion criteria:

1. Provide written informed consent prior to initiation of any study procedures
2. Able to understand and comply with planned study procedures and be available for all study visits
3. Males or non-pregnant females, 18-49 years of age, inclusive
4. In good health¹

¹As determined by medical history and physical examination to evaluate acute or currently ongoing chronic medical diagnoses or conditions, defined as those that have been present for at least 90 days that would affect the assessment of the safety of subjects or the immunogenicity of study vaccinations. Chronic medical diagnoses or conditions should be stable for the last 60 days. This includes no change in chronic prescription medication, dose, or frequency because of deterioration of the chronic medical diagnosis or condition in the 60 days prior to enrollment. Any prescription change that is due to change of health care provider, insurance company, etc., or that is done for financial reasons, if it is in the same class of medication, will not be considered a deviation of this inclusion criterion. Any change in prescription medication due to improvement of a disease outcome, as determined by the site principal investigator or appropriate sub-investigator, will not be considered a deviation of this inclusion criterion. Subjects may be on chronic or as needed (prn) medications if, in the opinion of the site principal investigator or appropriate sub-investigator, they pose no additional risk to subject safety or assessment of reactogenicity and immunogenicity and do not indicate a worsening of medical diagnosis or condition. Similarly,

medication changes after enrollment and study vaccination are acceptable provided there was no deterioration in the subject's chronic medical condition that necessitated a medication change, and there is no additional risk to the subject or interference with the evaluation of responses to study vaccination. Note: Topical and inhaled medications (with the exception of inhaled or nasal corticosteroids within 30 days prior to enrollment), herbals, vitamins, and supplements are permitted.

5. Oral temperature is less than or equal to 100°F
6. Pulse is 45 to 100 bpm, inclusive²

²Pulse can be 45 to 50 bpm, inclusive, if no other symptoms are present. Otherwise, pulse should be 50-100 bpm.

7. Systolic blood pressure is 85 to 150 mm Hg, inclusive
8. Diastolic blood pressure is 55 to 95 mm Hg, inclusive
9. White blood cell count is 3,900 cells/μL or greater³
10. Hemoglobin is 13.0 g/dL or greater (men) or 11.8 g/dL or greater (women)³
11. Platelet count is 135,000 cells/μL or greater³
12. Alanine aminotransferase is less than 45 U/L (women) or 62 U/L (men)³
13. Serum creatinine is less than or equal to 1.25 mg/dL (men) or 1.11 mg/dL (women)³

³Abnormalities in white blood count, hemoglobin, platelet count, alanine aminotransferase, and serum creatinine that are suspected to be due to laboratory anomalies may be repeated once to ensure accuracy; additionally, otherwise eligible subjects with grade 1 abnormalities in these values may be considered for enrollment if, in the opinion of the investigator (or clinician on the 1572), the abnormalities are not clinically significant and do not pose additional risk to the study or the volunteer.

14. Negative serum HIV antibody assay
15. Women of childbearing potential⁴ must use an acceptable contraception method⁵ from 30 days before study vaccination until 60 days after vaccination.

⁴Not sterilized via tubal ligation, bilateral oophorectomy, salpingectomy, hysterectomy, or successful Essure® placement (permanent, non-surgical, non-hormonal sterilization) with documented radiological confirmation test at least 90 days after the procedure, and still menstruating or <1 year has passed since the last menses if menopausal.

⁵Includes, non-male sexual relationships, abstinence from sexual intercourse with a male partner, monogamous relationship with vasectomized partner who has been vasectomized for 180 days or more prior to the subject receiving study vaccination, barrier methods such as condoms or diaphragms/cervical caps **with** spermicide, effective intrauterine devices, NuvaRing®, and licensed hormonal methods such as implants, injectables or oral contraceptives ("the pill").

16. Women of childbearing potential must have a negative urine or serum pregnancy test within 24 hours prior to study vaccination.

5.2 Subject Exclusion Criteria

1. Have immunosuppression as a result of an underlying illness or treatment, or use of anticancer chemotherapy or radiation therapy (cytotoxic) within 3 years prior to study vaccination
2. Have known or suspected active chronic autoinflammatory condition
3. Have known active neoplastic disease (excluding non-melanoma skin cancer) or a history of any hematologic malignancy
4. Have a history of persistent asthma, major anatomic nasopharyngeal abnormality, or sinus polyp disease due to chronic sinusitis⁶

⁶ *If a patient has a history of nasopharyngeal surgery such as, but not limited to rhinoplasty, tonsillectomy or sinus surgery, adequate healing time per the judgment of the investigator must occur prior to enrollment.*

5. Have known hepatitis B or hepatitis C infection
6. Have a history of alcohol or drug abuse within 5 years prior to study vaccination
7. Currently untreated or clinically unstable (in the opinion of the investigator) schizophrenia, bipolar disease, or other psychiatric diagnosis that may interfere with subject compliance or safety evaluations
8. Have been hospitalized for psychiatric illness, history of suicide attempt, or confinement for danger to self or others within 5 years prior to study vaccination
9. Have received corticosteroids (including oral, parenteral, inhaled, nasal, or intra-articular) of any dose within 30 days prior to study vaccination
10. Individual with PT serum IgG antibodies ≥ 20 IU/mL and/or PRN serum IgG antibodies ≥ 125 IU/mL
11. Unwilling to refrain from smoking tobacco for 28 days post vaccination
12. Receipt of immunoglobulin or blood derived products within 90 days of enrollment
13. Receipt of a vaccine against pertussis in the past 2 years
14. Receipt of a live vaccine within 30 days of study vaccination or an inactivated vaccine within 14 days of study vaccination
15. Planned vaccination with a licensed vaccine within 28 days of study vaccination
16. History of severe allergic reaction (e.g., anaphylaxis) or Bell's palsy, or Guillain-Barré syndrome, after a previous dose of any diphtheria toxoid-tetanus toxoid-, or pertussis-containing vaccine, or encephalopathy within 7 days of administration of a previous pertussis containing vaccine.
17. History of a progressive neurologic disorder
18. In close contact⁷ with children less than 1 year of age or contact with persons with known immunocompromising conditions

⁷ *Close contact includes sharing a household, serving as a healthcare worker, or working professionally in settings with repeated exposures.*

19. Receipt of *B. pertussis*-active antibiotics⁸ within 7 days prior to vaccination

⁸ *B. pertussis* active antibiotics include macrolides, fluoroquinolones, trimethoprim-sulfamethoxazole, tetracyclines

20. Known hypersensitivity to any component of the study vaccine.

21. Hypersensitivity to azithromycin, which may be used in the event of ongoing BPZE1 colonization

22. Any condition that, in the opinion of the investigator, might interfere with objectives of the study or safety to the individual

23. Acute illness, including temperature >100°F within one week prior to vaccination⁹

⁹ *Enrollment may be postponed if acute illness occurs; subjects must remain within the screening window, however, and must be rescreened if >30 days elapses prior to enrollment.*

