2.1.2 Phase 1b Clinical Study Results

The BPZE1 investigational liquid vaccine was safe in the higher doses and volumes used for nasal administration. Proportion of subjects having transiently BPZE1 colonized nasopharyngeal mucosa was not dose-related at 10^7 CFU or higher, but instead all dosage groups achieving 75% colonization rate or greater, and an overall combined colonization rate was observed for subjects from all randomized groups of over 80%. A dose response trend was observed, however, in the rate of colonization and clearance, with faster colonization rate and faster clearance rate being correlated with higher dosage. The serum antibody responses were strongly correlated to positive colonization, but there was no dose response. A small non-randomized group of subjects with

pre-existing high antibody titers for pertactin had a 33% rate of BPZE1 colonization after immunization with the 10^9 CFU dose.

There were no SAEs and any differences in AEs within randomized study groups, between placebo and the different dosages, were not detectable. The most frequent AEs were sneezing (n=55 episodes in 24 subjects), rhinorrhea (n=35 episodes in 22 subjects), nasal congestion (n=31 episodes in 19 subjects), cough (n=21 episodes in 16 subjects), and fatigue (n=21 episodes in 16 subjects). Efficacy results, included:

- *Colonization of mucosal surface:* The vaccine strain BPZE1 was isolated in a total of 29 randomized subjects, 10 in the 10^7 CFU dose group, 9 in the 10^8 CFU dose group, and 10 subjects in the 10^9 CFU dose group. Colonization was first detected on day 4-14 and lasted through day 11-28 after vaccination.
- *Immunogenicity:* Serologic responses (IgG and IgA) were measured to PT, PRN, FIM, and FHA and reported individually. In addition, responses were grouped by either:
 - ≥ 2 -fold rise in PT-specific IgG or IgA that was at least 4x greater than the minimum limit of detection (MLD) of the assay, or
 - ≥ 2 -fold rise in at least 2 antibodies targeting PRN, FIM, or FHA (IgG or IgA) that were at least 4x greater than the MLD

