To minimize the risk of transmission, the volunteers will stay at the study center for 2 hours after administration of the vaccine. In addition, volunteers with household or professional contact with infants below one year of age or household/professional contact with individuals with immunodeficiency will be excluded from participation in the study. The attenuated BPZE1 bacteria colonize the upper respiratory tract similarly to wild-type *B. pertussis*. Colonization of live organism will be assessed from a nasopharyngeal swab performed 28 days after administration to ensure all subjects are cleared of colonization. If a subject is not clear at day 29, a repeat nasal swab and culture will be performed at day 46. Chronic carriage of BPZE1 has not been reported (i.e., the vast majority of subjects have been clear at day 29 and no subject has had positive cultures at day 46) and is therefore not expected. Any subject who remains positive at day 46 will be provided a short course of azithromycin, which is clinically used to eradicate *B. pertussis* from the nasopharynx. Azithromycin will be prescribed by a study physician and filled by the hospital pharmacy or the patient's desired pharmacy at no cost to the subject.

Furthermore, in animal studies, when female mice were vaccinated with BPZE1 shortly before mating, no negative effect on either the pregnancy or their offspring was observed. The offspring were protected against *B. pertussis* challenge, based on evaluation of the lungs at necropsy.[16]

[REDACTED]

2.3.1.3 Risks to the Environment or Potential for Interaction with wild-type *B. pertussis* strains

Detailed information about the [REDACTED] BPZE1 is available in the environment risk assessment located in the investigator's brochure.

To avoid accidental exposure to the environment and to study staff, actions should be taken to minimize generation of aerosols, since the bacteria are strictly respiratory tract organisms. Staff members should wear eye-protective glasses during the vaccination. Persons handling BPZE1 should wear gloves and must practice standard hand hygiene before touching their skin or eyes.

[REDACTED]

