7.2 Enrollment/Vaccination (Visit 1, Clinic Visit [Day 1])

- Subject's willingness to participate will be reconfirmed and documented in the subject's study records prior to performing any further study procedures, including administration of the study vaccination.
- Eligibility criteria will be reviewed with subjects prior to study vaccination to ensure continued eligibility.
- Complete medical history and any updates obtained by interview of subjects since the screening visit will be reviewed with subjects prior to study vaccination to ensure continued eligibility.
- All concomitant medications will be reviewed with subjects prior to study vaccination for accuracy and completeness. Any new concomitant medications taken since the screening visit will be reviewed with subjects and assessed for continued eligibility prior to study vaccination. Medications reported in the eCRF are limited to those taken within 30 days prior to study vaccination.
- Vital signs, including oral temperature, pulse, and blood pressure, will be obtained prior to study vaccination. Vital signs assessed on Day 1 will be considered as baseline. Subjects must not eat or drink anything hot or cold, or smoke within 10 minutes prior to taking oral temperature.
- A limited physical examination will be performed, focused on the nasopharynx, oropharynx, and lungs prior to study vaccination; in addition, a targeted physical examination will be performed, if indicated, based on review of interim medical history, by a study clinician.
- A urine or serum pregnancy test will be performed within 24 hours prior to study vaccination on all women of childbearing potential. Results must be negative and known prior to randomization and first study vaccination.
- Approximately 10 mL of venous blood will be collected immediately prior to study vaccination for baseline antibody assays.
 - For subjects who consent to additional future use samples, approximately 24 mL of venous blood will be collected immediately prior to study vaccination for PBMC isolation and possible future research.

-
- Subjects will be enrolled in AdvantageEDCSM and assigned randomly to a treatment arm prior to study vaccination.

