4.3. Selection of Study Population

The study population for DMID protocol 17-0010 is males and non-pregnant females, 18 to 49 years old, inclusive, who are in good health and meet all eligibility criteria. Potential subjects will be screened from the general population at VUMC by history, physical exam, clinical laboratory tests including White Blood Cells (WBC), Hemoglobin (Hgb), platelets, serum IgG antibodies, alanine aminotransferase (ALT), Creatinine, and Human Immunodeficiency Virus (HIV), and a urine or serum pregnancy test. Potential subjects with close contact, defined as sharing a household, serving as a healthcare worker, or working professionally in settings with repeated exposures, with children less than 1 year of age or with persons with known immunocompromising conditions will be excluded. Otherwise eligible potential subjects experiencing an acute illness, including temperature $>100^{\circ}\text{F}$, will be eligible for postponed enrollment within the screening window or rescreening once symptoms resolve.

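### The close-contact exclusion (criterion 18) covers contact present at enrolment but states no period after vaccination, and its three statements differ on immunocompromised contacts

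*Protocol*

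**What the plan says.** Criterion 18 in protocol section 5.2 excludes a subject who is in close contact "with children less than 1 year of age or contact with persons with known immunocompromising conditions". Its footnote 7, attached to the first mention of contact, reads: "Close contact includes sharing a household, serving as a healthcare worker, or working professionally in settings with repeated exposures". Neither the criterion nor the footnote mentions expected contact or a period after vaccination.

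Section 2.3.1.2 states the rule again, among the measures to reduce transmission: "volunteers with household or professional contact with infants below one year of age or household/professional contact with individuals with immunodeficiency will be excluded". SAP 4.3 states it a third time, defining close contact by household, health-care work "or working professionally in settings with repeated exposures, with children less than 1 year of age or with persons with known immunocompromising conditions". Neither adds a time window.

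Other exclusions in section 5.2 do look forward. Criterion 11 is "Unwilling to refrain from smoking tobacco for 28 days post vaccination" and criterion 15 is "Planned vaccination with a licensed vaccine within 28 days of study vaccination".

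The last eligibility check is on Day 1, under section 7.2: "Eligibility criteria will be reviewed with subjects prior to study vaccination to ensure continued eligibility". In Phase 1b (section 2.1.2), colonisation was first detected on day 4-14 and "lasted through day 11-28 after vaccination". Section 2.1.1 gives the same ranges for Phase 1a.

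**The concern.** The rule protects third parties, and the hazard to them begins only after the dose. A subject with no relevant contact on Day 1 can acquire one while carrying the strain. Two examples are a man whose partner is due in two weeks and a student who starts a hospital or day-care placement the following week. Read literally, neither meets criterion 18 on Day 1.

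A second problem is independent of timing. The three statements do not describe the same set of immunocompromised contacts, so one volunteer can be eligible under one section and ineligible under another. Section 5 allows no exemptions from the eligibility criteria, so the wording has to settle the matter.

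At stake is whether a stated safeguard covers the period it was written for. The people concerned are infants, whom the protocol describes as especially vulnerable, and immunocompromised people. They have no part in the consent.

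**Working it through.** **Timing.** Set the rule beside the carriage data.

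- Last application of the rule: Day 1, before dosing (section 7.2). The visit lists in sections 7.3 and 7.4 include no question about new contacts.
- Carriage in Phase 1: first detected on day 4-14, ending on day 11-28 (sections 2.1.1 and 2.1.2). Section 2.3.1.2 adds that nearly all subjects were clear at day 29 and none was culture-positive at day 46.
- The hazard period therefore falls wholly after the last check.

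**Do other provisions close the gap?**

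- Criterion 22 gives the investigator discretion over conditions bearing on the study objectives or the individual's safety. It does not mention contacts.
- The Day 1 review re-applies the same present-tense wording.
- Section 5.3.3 lists loss of eligibility as a reason for withdrawal, but withdrawal after a single live dose does not end carriage.
- The 2-hour stay after dosing ends before the earliest recorded detection of colonisation.
- A subject who is herself pregnant is excluded, so a newborn would arrive through a partner, another household member or adoption.

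**The three statements on immunocompromised people.**

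| Place | Contact that excludes |
|---|---|
| Criterion 18 | contact, unqualified; footnote 7 is attached to the infant clause |
| Section 2.3.1.2 | household or professional contact |
| SAP 4.3 | close contact as defined, for infants and immunocompromised people alike |

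A volunteer who sees an immunocompromised friend socially is excluded by the letter of the first row and not by the other two.

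**Size.** The plan's own figure comes first. Section 2.1.2 reports colonisation in 10, 9 and 10 subjects across three dose groups of 12: (10 + 9 + 10)/(3 × 12) = 29/36 = 80.6%. This reproduces the stated rate of over 80%.

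Inputs for the estimate:

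- BPZE1 recipients: 15 + 15 + 5 = 35 (section 4, Table 2).
- Colonised fraction: 29/36 (Phase 1b, liquid formulation).
- Window: 28 days, the upper end of the Phase 1 carriage range.
- Yearly rate of gaining a relevant contact: 3-6%. This is an assumption; the documents give no figure.

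Expected contact opportunities = 35 × (29/36) × (28/365) × yearly rate.

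- At 3%: 35 × 0.806 × 0.0767 × 0.03 = 0.065
- At 6%: 35 × 0.806 × 0.0767 × 0.06 = 0.130

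The range is about 0.06-0.13 for the whole trial. The result is proportional to the assumed rate: each percentage point per year adds 35 × 0.806 × 0.0767 × 0.01 = 0.022. Using 10/12, the Phase 1b rate at each of the two doses studied here, gives 0.07-0.13.

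**The case against.** The strongest reply is that the practical risk is very low and may already be handled.

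- Section 2.3.1.2 expects no induced cough and considers transmission highly unlikely. Section 2.3.1.3 reports no cross-contamination between volunteers and no observed risk to family members in Phase 1. This stands, and it limits the severity. It does not change what the criterion says, and the sponsor still judged the risk worth an exclusion.
- Consent pages are not in the public file and the manual of procedures is not supplied. Either could tell subjects to avoid infants and immunocompromised people after dosing. This stands as a limit on what can be concluded.
- An investigator who knows the purpose of the rule need not enrol an imminent parent, and footnote 7 says *includes*, so its list is open. A reader might infer that such a volunteer is eligible beyond dispute. That goes too far: discretion exists, but nothing directs it to contacts.
- The second mention of contact in criterion 18 may be shorthand for the footnoted term. That is a plausible reading, and one clause would confirm it.

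A reader might also take the Day 46 culture and Day 50 call as evidence of a 45-day hazard in all 35 recipients, which gives 35 × (45/365) × 3-6% = 0.13-0.26. The documents do not support this. Those visits are contingencies, Phase 1 carriage ended by day 11-28, no subject was positive at day 46, and not every recipient was colonised.

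**Conclusion.** The gap in wording is real and of low severity. Criterion 18 does not state that it applies to contact expected after vaccination, although carriage, the reason for the rule, occurs only then. The inconsistency over immunocompromised contacts is also real and rests on the text alone.

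The size is about 0.06-0.13 expected contact opportunities among 35 recipients. This rests on the unsourced 3-6% yearly rate, on the Phase 1b colonisation rate carrying over to the lyophilised product, and on independence between gaining a contact and being colonised. It counts every colonised subject as a carrier for the full 28 days. Since carriage began on day 4-14 and could end by day 11, the figure leans high for the assumed rate. These are opportunities for contact, not transmissions; a reader might take each as an infant or immunocompromised person exposed to the strain, and neither the documents nor the arithmetic shows that.

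**What to change.** 1. Reword criterion 18 to cover current or anticipated close contact over a stated period after vaccination. The sponsor should set that period from its own carriage data and the Day 29 culture plan; none is proposed here. It should be fixed in advance, because a condition that depends on a later culture result cannot be assessed at screening.
2. State whether footnote 7 applies to both infants and immunocompromised people.
3. Bring section 2.3.1.2 and SAP 4.3 into line with the revised criterion.

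No new visit or check is needed: the Day 1 eligibility review would then ask about expected contact as well. If the consent form or manual of procedures already gives contact advice, a cross-reference from section 5.2 would help.

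The cost is a short protocol amendment, a matching edit to the SAP and one more screening question. A few volunteers, such as expectant fathers and people about to change jobs, would become ineligible.
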